In year 2, We will recruit adult patients (aged 40-70; n=54) of the UPMC General Internal Medicine-Oakland (GIMO) practice not meeting the US aerobic activity goal of 150 minutes/ week of at least moderate intensity physical activity who can safely increase physical activity without supervision and have who also have at least one of the following common cardiometabolic risk factors for which improving physical activity levels can be beneficial (high blood pressure: > 129 mm hg SBP or > 89 mm hg DBP or medication use, high fasting glucose: > 100 mg/dl or high HbA1c: ≥ 42 mmols/mol or medication use, overweight/ obesity: BMI ≥ 25 kg/m²). As low physical activity levels have been associated with numerous poor cardiometabolic health outcomes, the primary intervention goal will be achievement of the US physical activity goal. Intervention materials will be developed using a patient/provider centered approach and delivered weekly over 3 months via the existing GOALS online platform with participants self-tracking behavior (using a commercial wrist worn activity monitor). An additional 9 months of "maintenance" support will be provided via the GOALS platform and email/phone contact from a coach. Using an online approach will reduce staff and participant burden and will allow for wider dissemination of the program. A prospective randomized, active control design will be used to determine changes in the primary outcomes of objectively measured step counts, % of individuals meeting the moderate-vigorous physical activity goal. Active

control participants will be given a commercial wrist worn activity monitor and information on the CDC activity recommendations.

4. * What kind of study is this?

Single-site study

5. * Will an external IRB act as the IRB of record for this study?

Yes No

6. * Local principal investigator:

[name]

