We will work with the UPITT Community Research Advisory Board (CRAB) during months 1-4 to develop recruitment materials. Modification of existing ActiveGOALS materials will take place in months 1-8 (including updated coaching materials). This will also include full-integration of a PAT device. In months 8-12 we will develop the 9 monthly maintenance sessions. Staff hiring and training will take place in months 8-12; this will include at least 1 student worker to help with recruitment and retention and 1 graduate student coach with a background in exercise medicine or physical activity and health. All development will be completed by the end of year 1 of funding.

Screening: Phone screenings and EHR records will be used to verify eligibility status. During the phone screen participants will be asked to verify their activity status and given a short disability screener to ensure their ability to safely participate. If eligibility for cardiometabolic risk cannot be confirmed via EHR or by a physician potential participants will be able to complete screening in-person, which will involve height and weight measurement, blood pressure reading, and onsite Hba1c testing (if needed) by trained clinic staff. Less invasive screening procedures will be performed first and the in-person screening will end once eligibility is confirmed- regardless of whether all procedures were completed. Height and weight will be taken first, followed by blood pressure, and then Hba1c.

Weight: Weight will be measured twice without shoes on using a portable scale placed on a hard, flat surface. The subject will be asked to stand in the middle of the scale without touching any surface with eyes straight ahead. The subject will be asked to step down from the scale between measures. If the measures are more than 0.5 pounds apart, a third measure will be taken.

Height: Height will be measured twice without shoes. The subject will be asked to stand erect under the stadiometer with eyes straight ahead. Subjects will be asked to step down between measures. If the measures are more than one-half inch apart, a third measure will be taken.

Blood Pressure: Blood pressure will be measured with a validated automated cuff in the right arm with the patient seated comfortably with the right arm resting on a

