table. Participants will be asked to rest quietly with feet flat on the floor for five minutes. The cuffed arm will be raised for 5 seconds after each inflation and a wait of 30 seconds will occur between each blood pressure reading. Blood pressure will be repeated twice with the average computed. If it is not possible to measure blood pressure in the right arm, the left arm should be utilized and noted in the patient record.

HbA1c: HbA1c will be assessed using a point of service hba1c monitor. Participants will be seated for the finger stick. Hand warmers may be used prior to the finger stick to ensure good blood flow. A sterile lancet will be used to prick the 3rd or 4th finger tip of the non-dominant hand- after the site has been prepped with a 70% isopropyl alcohol swab and is thoroughly dry. The first drop of blood will not be used, if needed the finger will be gently squeezed to obtain a second drop of free-flowing blood. A fresh finger stick will be applied and inserted into the monitor. Results will be available within 5-10 minutes.

Intervention Delivery: ActiveGOALS uses online self-directed once a week sessions with brief remote personalized e-coaching support. Social-cognitive behavior change theory and related strategies, including barrier recognition and problem-solving are included. There are 13 (20-25 minute) structured educational lessons with interactive workbook pages delivered via the GOALS online platform. After the 13 week “core intervention”, participants will continue to have access to resources on ActiveGOALSV2 for 9 more months and will receive once a month contact including a semi-personalized email from their coach and a link to online materials on a specific behavior maintenance topic (10 minutes in length). Printable workbook pages, resources, and tracking tools will also be available. The topics for the maintenance materials will be determined from output of satisfaction/ experience questionnaires administered to current ActiveGOALSV1 participants (PCOR K12 funded project) and already developed proven maintenance materials from DPP and DPP GOALS.

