Brief weekly motivational feedback from a coach (with a physical activity and health or exercise science background) will be provided during the 13 week “core” intervention program via the ActiveGOALSV2 platform. Coaches will also access study administered participant PAT accounts. The coach will set goals in the PAT program to match weekly study goals and will utilize other program features (like reminders and push messaging) according to protocol developed in yr 1 of funding).

The primary behavior tracking tool will be a wrist worn PAT. However, participants will also be provided with paper and online tracking tools for physical activity to track/ report their step counts and activity minutes. I am currently working with Fitbit® monitors in other clinical patient population studies which we plan to use in this study. Currently, Fitbit devices are the most commonly used brand in the US and have been shown to validly and reliably record step counts.[69,70] As done in other studies, we will set-up PAT accounts for participants.

Outcome Assessment: All outcome measures will be collected at all time points (baseline, 6 and 12 months post-intervention) for all participants. After being consented, physical activity levels, clinical, and questionnaire measures will be

collected. Clinic visits should take 30-45 minutes to complete. Blood draws will be performed at a Quest™ lab.

Primary outcomes: Average step counts/day and time spent in moderate-vigorous (MV) physical activity will be collected from validated research grade body-worn PATs; ActiGraph wGT3X+ accelerometer (ActiGraph LLC; Pensaco-la, FL) worn on the waist during waking hours for the 7 days after a clinic visit. These accelerometers have been validated for assessing time spent in physical activity intensities and step counts in laboratory[76-81] and field settings[80,82-84] and are used to validate commercial monitors.[69,70] Data recorded in 1 second epochs will be output as activity counts [85,86] and converted to step counts and time spent in MV physical activity using accepted cut-points.[78,86]

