Support. Coaches will be available through secure messaging within the GOALS online platform; replies are sent within two business days. Participant progress will be reviewed by the coach at least weekly. Notes will be sent to the participant either in reply to a message or in response to an issue the coach has noted (e.g. failure to log in, tracking problems, etc.). Participants who do not log in for two or more weeks will be called by telephone. If approved by the participant, PCPs are informed when their patients are enrolled. PCPs also receive 3 progress reports (4-6 weeks post-baseline, after the 6 month assessment, and after the 12 month assessment) and are contacted if questions or concerns arise that cannot be resolved by the research team.

3. * Will blood samples be obtained for research purposes?

Yes No

*** Provide the volume per withdrawal, total volume and frequency, and qualifications of individual performing the procedure:**

If needed an in-person finger stick will be obtained to determine eligibility to participate based on Hba1c and will only be done once. A 5 μ L sample of blood will be taken after finger puncture with a sterile lancet. Results will be reported in less than 10 minutes. This will be done by a trained staff person.

All venipuncture blood draws will be performed at a Quest lab by Quest staff. Quest staff are certified and experienced in drawing blood. This will be performed 3 times during the study (baseline, 6-months, and 12-months visits). Less than 15ml of blood will be drawn at each assessment.

Consent Process

Enter N/A in response to the following questions if a Waiver of Consent is requested for all research activities or if no subjects are being enrolled.

1. * Indicate where the consent process will take place and at what point

consent will be obtained:

After performing certain screening procedures, but prior to performing any of the research interventions/interactions informed consent will be obtained for the main study.

Screening consent: Screening consent will be obtained verbally over the phone or in-person for in-person screening. The PI or trained study staff will use a script to first obtain consent and then perform a short screening. If a participant must complete a second in-person screening for cardiometabolic eligibility confirmation then an addition written consent for those screening measures will be done prior to the in-person screening.

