glucose level in the diabetes range or greatly elevated lipid results will be

- 1) Given their results with a clear explanation of the problem, and
- 2) Advised to follow up with their health care provider as soon as possible.

6. Describe the potential benefit that individual subjects may experience from taking part in the research or indicate if there is no direct benefit. Do not include benefits to society or others:

Participants may not receive any benefit from taking part in this project. Intensive lifestyle interventions containing a physical activity component have been shown to reduce the onset of type 2 diabetes and the metabolic syndrome. Participation in this study may help reduce the risk of developing diabetes and/or cardiovascular disease. Participation in this study may benefit society by leading to the development of a feasible clinical prescription program for physical activity and sedentary behavior improvement that could reduce risk factors for diabetes and cardiovascular disease as well as other conditions for which physical activity has been shown to be beneficial.

Accomplishing the goals set out by this proposal will have the potential for making a feasible prescription program for physical activity and sedentary behavior improvement available for use within clinical practice (and throughout large health systems. This information could be used toward the development of future intervention strategies that are feasible for adult clinical care patients.

7. Do you anticipate any circumstances under which subjects might be withdrawn from the research without their consent?

Yes No

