*** Describe the circumstances and any procedures for orderly termination:**

If for some reason they are unable to complete the majority of the sessions. If their health status changes, it is also possible that their referring physician could withdraw their permission for participant.

8. Describe procedures that will be followed when subjects withdraw from the research, including partial withdrawal from procedures with continued data collection and data already collected:

Any identifiable research or medical information recorded for, or resulting from, participation in the study prior to the date the participant formally withdraws consent may continue to be used and disclosed by the investigators for the purposes described in the study protocol.

Ancillary Reviews

1. Ancillary reviews or notifications selected below are required based on previous answers to questions. If a selection is incorrect, return to the appropriate page and adjust the answers to questions on that page:

- Conflict of Interest (**COI**)
- Clinical and Translational Research Center (**CTRC**)
- Data Security
- Honest Broker
- UPMC Investigational Drug Service
- Pitt Medical School Review
- Pitt Nursing School Review
- Pitt+Me
- IND & IDE SUPPORT (**IIS**)
- Radioactive Drug Research Committee (**RDRC**)(study involves the evaluation or use of procedures that emit ionizing radiation)
- RCCO Business **Manager** (required for industry sponsored studies)
- Religious Directives
- Scientific Review
- Health Record Research Request (**R3**) (required if using UPMC clinical data and authorization for other UPMC data sources for research)
- UPMC Office of Sponsored Programs and Research **Support** (using UPMC facilities and/or UPMC patients during the conduct of the study)

2. Additional ancillary reviews the PI may choose to include as needed for the research:

- Human Stem Cell Oversight (**hSCRO**)
- Institutional Biosafety Committee (**IBC**)(study involves deliberate transfer of recombinant or synthetic nucleic acid molecules)

Good Clinical Practice (GCP) Training

1. * Regardless of funding source, is this study a clinical trial (as defined by the NIH)?

Yes No

ClinicalTrials.gov Information

Visit the University of Pittsburgh Office for [ClinicalTrials.gov website](#) or contact [contact] for further information.

1. * Was this study registered, or will it be registered, on ClinicalTrials.gov?

Yes No

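### Participants can be withdrawn from the research for missing most sessions, which only the ActiveGOALS arm has, although outcomes are promised for everyone

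*Protocol*

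**What the plan says.** Risk and Benefits, item 7 of the Protocol asks: "Do you anticipate any circumstances under which subjects might be withdrawn from the research without their consent". The answer gives two circumstances: "If for some reason they are unable to complete the majority of the sessions", and the referring physician withdrawing permission after a change in health. Item 8 asks what happens after withdrawal, including continued data collection. Its answer covers only information recorded "prior to the date the participant formally withdraws consent may continue to be used and disclosed by the investigators".

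Sessions are described only as part of ActiveGOALS. Under Research Activities, Intervention Delivery: "ActiveGOALS uses online self-directed once a week sessions with brief remote personalized e-coaching support". Under Development: "In months 8-12 we will develop the 9 monthly maintenance sessions". In the other arm (Basic Study Information, item 3), "control participants will be given a commercial wrist worn activity monitor and information on the CDC activity recommendations". Study assessments are called visits, not sessions.

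Two other passages bear on the point. Outcome Assessment says: "All outcome measures will be collected at all time points (baseline, 6 and 12 months post-intervention) for all participants". Support gives the response to non-use: "Participants who do not log in for two or more weeks will be called by telephone". It does not mention withdrawal.

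SAP 6.1.6 and Protocol, Study Design, item 8 plan a mixed model with group, time, their interaction and a random subject effect, assuming data are missing at random.

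**The concern.** The ground depends on behaviour after randomisation and can be met in one arm only. It is worded as withdrawal from the research, not from the programme. It therefore sits badly with the promise to collect outcomes from all participants, and item 8 does not settle whether someone withdrawn this way is still assessed. No threshold date or procedure is given. Sessions could mean the 13 core lessons or also the 9 maintenance sessions, so removal could fall before or after the 6-month visit.

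The analysis does not protect against this. Session completion is not in the model, and controls have no session count to enter as a covariate. Participants are grouped as randomised, but no sentence commits to following and analysing everyone randomised. No analysis is planned for data not missing at random. If completers improve more than non-completers, the estimate overstates the effect of being offered ActiveGOALS.

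**Working it through.** **Planned sample size.** From Study Design, item 8: difference 2000 steps/day, SD 2200, two-sided .05, power .80, 20% attrition. A two-sample t-test needs 20.002, so 21 per arm. 21/0.80 = 26.25, so 27 per arm and 54 in total. The plan's figure reproduces, taking 1:1 allocation (the ratio is not stated).

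**Assumptions for the bias.** The documents give no withdrawal share, timing or outcome difference. I assume 27 per arm, SD 2200, visits at 0, 6 and 12 months, within-person correlation ρ = 0.6, no other missing data and no true effect. The k lowest on a completion score leave the ActiveGOALS arm. The score has correlation r with the person's own 0–12 month change.

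**Formula.** A missing-at-random model corrects only for what the observed visits explain. What remains is

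bias = r × 2200 × c × m

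- m is the expected mean standardised score of those kept: 0.203, 0.315 and 0.636 for k = 3, 5 and 11 of 27.
- Removed before month 6 (only baseline observed): c = (1 + ρ) × √((1 − ρ)/2) = 1.6 × 0.447 = 0.716.
- Removed after month 6: c = (1 + ρ/(1 + ρ)) × 0.447 = 1.375 × 0.447 = 0.615.

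Example, k = 5, r = 0.3, before month 6: 0.3 × 2200 × 0.716 × 0.315 ≈ 149 steps/day.

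**Results** (steps/day towards ActiveGOALS, r = 0.3 / 0.5; 6000 simulated trials per cell, simulation SE 7–8):

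| Removed | Before month 6: formula | simulated | After month 6: formula | simulated | Type I error |
|---|---|---|---|---|---|
| 3 of 27 | 96 / 160 | 95 / 157 | 82 / 137 | 79 / 138 | .049–.057 |
| 5 of 27 | 149 / 248 | 134 / 242 | 128 / 213 | 120 / 216 | .054–.067 |
| 11 of 27 | 300 / 501 | 303 / 496 | 258 / 430 | 256 / 430 | .074–.122 |

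The simulated 134 is about two simulation SEs below the formula; the other cells agree closely. Against 2000, the 5-of-27 case is 120/2000 = 6% to 242/2000 = 12%. At r = 0 the bias is −6 to +8. With follow-up kept it is −4 to +2, and type I error is .045–.049.

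If completion is instead correlated with the 12-month value given baseline, 20% withdrawn gives 186 to 310 before month 6 and 120 to 214 after it (r = 0.3 to 0.5).

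**With a true effect.** Let 22 completers gain 2000 and 5 non-completers gain 0, with the same gains at month 6. As randomised, the effect is 22 × 2000/27 = 1630.

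- Removed before month 6, the model returns the completers' 2000 (simulated 2014, +24%).
- Removed after month 6, it returns 2000 − 0.375 × (2000 − 1630) = 1861 (simulated 1854, +14%), where 0.375 = 0.6/1.6.
- If non-completers gain 1000, the as-randomised effect is 1815, against simulated 2011 (+11%) or 1933 (+6%).
- If they gain 2000, the overstatement is about 0.

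**Activity goal.** If 20% are removed and none of them met the goal, a true 20% appears among those observed as 0.20/0.80 = 25%.

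**The case against.** The strongest reply is that the Outcome Assessment sentence is a schedule and item 7 is an exception to it. The plan already allows 20% attrition, so the schedule was never a promise of complete data. Item 7 speaks of being unable to complete sessions and of what might happen, and the practical response to non-use is a telephone call. The SAP plans descriptions of missing data and attrition patterns, which partly covers a count by arm. The main consent form is not shown and may address follow-up.

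The size can also be challenged. People unable to complete sessions may miss visits anyway. If half of the 5 would be lost regardless, the rule itself adds about 75 to 129 steps/day, or 4–6% of 2000. The 11-of-27 case is 41% of the arm, twice the planned attrition, and the +24% needs non-completers to gain nothing.

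Much of this stands as a limit on size: use is discretionary and its frequency unknown. It does not remove the defect. An exception that only one arm can meet, tied to adherence, with continued assessment left unstated, differs from ordinary attrition. Describing attrition does not correct it.

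**Conclusion.** The concern holds. The Protocol allows withdrawal from the research on an adherence ground that only ActiveGOALS participants can meet, and this is not reconciled with outcome collection for everyone.

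The harm is conditional. The ground must be used, it must end assessment, and non-completers must improve less than completers; the opposite relation would reverse the direction. With 3 to 5 of 27 removed, the bias is modest: about 79 to 242 steps/day under the main assumptions, with type I error .05–.07. Error near .12 appears only with 11 removed. If non-completers gain little, the overstatement of a real effect could reach 14–24%. This should be fixed; confidence is medium, because every input on withdrawals is assumed.

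**What to change.** Reconcile item 7 with the Outcome Assessment text. Remove session non-completion as a reason for withdrawal from the research, and leave the physician-permission reason as it is. Suggested wording: *Participants who do not complete sessions remain in the study and are invited to the 6- and 12-month assessments; every randomised participant is analysed in the assigned group.* In item 8, state that assessments continue unless the participant withdraws consent to them.

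The Protocol estimated completion of the primary analyses by 12/31/2022 and the cover is dated November 2025, so follow-up may be over. In that case, report by arm how many were withdrawn on this ground and their last visit. Add a sensitivity analysis, labelled post hoc, for data not missing at random. For example, shift missing ActiveGOALS 12-month values from the model prediction down to no change from baseline. If the count is zero, reporting it settles the matter.

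The cost is a wording amendment. Visits and payments are already planned for all 54, so the extra burden is staff effort to bring back non-adherent participants, and probably a smaller estimated effect. After follow-up, it is one count table and one analysis.

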Coverpage

Title: Advancement of Clinical Referral to Physical Activity for Cardiometabolic Disease Prevention

Brief Title: The Clinical Referral to Activity Study

NCT: NCT04743856

Date Created/Modified: November 3, 2025

Statistical Analyses

6.1.6 Statistical Analyses: For our primary outcomes, we hypothesize that participants randomized to ActiveGOALSV2 + PAT will have significantly larger (a) increases in step counts/day and % meeting MVPA goal of 150 minutes/week (to 12 months) compared to the active PAT control group. Descriptive analyses and graphic displays will be used to identify outliers, missing data, and pattern of attrition. To ensure rigor, the primary analytic strategy will be a linear or generalized mixed-effect models approach in which treatment group, time, and time by group interaction are treated as fixed effects, and subject is treated as a random effect to account for individual subject variability (two sided hypothesis test; .05 level). Mixed models are applicable to longitudinal datasets that contain missing observations, (assuming data is missing at random). Regression modeling will be conducted to adjust for important covariates. We will perform similar analyses to examine changes in secondary outcomes. Descriptive statistics on patient experience, beliefs/attitudes related to maintenance of PA changes, and program cost will also be reported. Mixed models are used to help account for missing data and no adjustments will be made for multiple comparisons.
